#### **5.2.5.1 Dose Interruptions**

Appropriate follow up assessments should be done until adequate recovery occurs as assessed by the Investigator. Criteria required before treatment can resume are described in Dose Delays (Section 5.2.5.2).

Doses may be held as needed until toxicity resolution. Depending on when the AE resolved, a treatment interruption may lead to the patient missing all subsequent planned doses within that same cycle or even to delay the initiation of the subsequent cycle.

If the AE that led to the treatment interruption recovers within the same cycle, then re-dosing in that cycle is allowed. Doses omitted for toxicity are not replaced within the same cycle. The need for a dose reduction at the time of treatment resumption should be based on the criteria defined in Dose Modifications (Section 5.2.5.3), unless expressly agreed otherwise following discussion between the Investigator and the SMC.

In the event of a treatment interruption for reasons other than treatment-related toxicity (e.g. elective surgery) lasting >28 days, treatment resumption will be decided in consultation with the SMC.

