#### 5.2.5.2 Dose Delays

Patients experiencing Grade 3 or 4 potentially treatment related toxicity or intolerable Grade 2 toxicity despite supportive care should have their treatment interrupted/delayed. Appropriate follow-up assessments should be done until adequate recovery (or until deemed irreversible) occurs as assessed by the Investigator. A treatment delay of more than 4 weeks due to lack of recovery will result in discontinuation of the patient from the treatment, unless continuation (with dose reduction) upon subsequent recovery is considered in the patient's best interest by the investigator (e.g. proven clinical benefit).

A new cycle of treatment may begin only if:

- a. ANC ≥ 1000/µL
- b. Platelet count ≥ 100,000/µL
- c. Hemoglobin ≥ 8.5 g/dL
- d. Non-hematologic toxicities have returned to baseline or Grade ≤ 1 severity (or, at the investigator discretion, Grade ≤ 2 if not considered a safety risk for the patient).

Withhold scheduled dose for liver function test related AEs (including asymptomatic) Grade  $\geq 3$  until return to baseline or Grade  $\leq 1$  severity. In cases of potential liver injury, consultation with a hepatologist should be considered in the decision to initiate treatment with anti-inflammatory medications.

If these conditions are not met, treatment must be delayed by 1 week. If, after a 1-week delay, all toxicities have recovered within the limits described above, treatment with study drugs, can be resumed. Both study drugs should be delayed simultaneously if applicable. If the patient has not recovered after 1 week of delay, treatment may be delayed by 1 more week. However, initiation of the next cycle can only be delayed by a maximum of 4 weeks (28 days). Therefore, if persisting toxicity does not allow for the resumption of treatment, the patient will be permanently discontinued.

For all ≥ Grade 3 hematological or non-hematological AEs that are NOT study drug-related, after consultation with the Medical Monitor and at the discretion of the treating physician, study drug dosing may be continued.

Elevation of amylase and/or lipase without clinical and/or radiographic evidence of pancreatitis are not considered DLT, and the patient can resume treatment at any grade at the discretion of the treating physician in consultation with the PI.

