## 5.2.5.3.1 Adverse Drug Reactions Requiring M6620 Treatment Discontinuation or Modifications

In the case of occurrence of an AE attributed to M6620, treatment may be interrupted and may resume when all toxicities have returned to Grade 2 or less, at the discretion of the Investigator. Except for participants in Part A during the DLT observation period, doses of M6620 may be reduced after occurrence of a related AE using the following guidelines, any exceptions to this dose modification criterion will need to be agreed between the PI and IND Office:

- a. For Grade 4 hematologic toxicity: the dose of M6620 will be reduced by 25%.
- b. For Grade 3 non-hematologic toxicity: M6620 will be discontinued.
- c. For Grade 4 non-hematologic toxicity: M6620 will be discontinued.

Guidelines for dose modification for toxicity are provided below. The final dose reduction or delay for each participant may be determined by the Investigator. However, these guidelines provide the minimum dose reduction or delay criteria. Additionally, if a participant who is responding to treatment experiences toxicity even after 2 dose reductions, the participant may continue to receive treatment if in the judgment of the Investigator it is in the best interest of the participant. In this case the dose of M6620 will further be reduced by at least 25%.

In case of M6620 Grade 3 or higher toxicity (excluding fatigue or nausea/vomiting/diarrhea adequately managed by supportive care), treatment will be interrupted and may be resumed when all toxicities have returned to Grade 2 or lower, at the discretion of the Investigator.

For the following hematologic toxicities, once the toxicity has returned to Grade 2 or lower, dosing can be resumed with 1 dose level reduction. If, after 1 dose level reduction, any of the below drug-related hematologic toxicities are subsequently observed, then dosing may be resumed with 2 dose level reductions:

- a. Grade 4 thrombocytopenia;
- Febrile neutropenia (growth factor support, per site protocol, may be used in lieu of dose reduction) except during the DLT assessment period prior to occurrence of a DLT. Once a DLT has occurred, it is acceptable to use growth factor support even during the DLT period;
- c. Grade 4 neutropenia lasting more than 7 days.

If any of the drug-related toxicity listed below is subsequently observed, the M6620 dose will be reduced by 1 dose level:

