## Dermatological irAEs

Grade of Rash	Initial Management	Follow-up Management	
Grade 1 to 2 Covering ≤ 30% body surface area	Continue avelumab therapy. Symptomatic therapy (for example, antihistamines, topical steroids)		
Grade 3 to 4 Grade 3: Covering > 30% body surface area; Grade 4: Life-threatening consequences	Permanently discontinue for	Taper steroids over at least	

Pulmonary irAEs			
Grade of Pneumonitis	Initial Management	Follow-up Management	
Grade 1 Radiographic changes only	Consider withholding avelumab therapy Monitor for symptoms every 2 to 3 days Consider Pulmonary and Infectious Disease consults	Treat as Grade 2 or Grade	
Grade 2 Mild to moderate new symptoms	Withhold avelumab therapy Pulmonary and Infectious Disease consults Monitor symptoms daily; consider hospitalization 1.0 to 2.0 mg/kg/day prednisone or equivalent Add prophylactic antibiotics for opportunistic infections Consider bronchoscopy, lung biopsy	over at least 1 month, and then resume avelumab therapy following steroids taper If not improving after 2	
Grade 3 to 4 Grade 3: Severe new symptoms; New/worsening hypoxia; Grade 4: Life-threatening	Permanently discontinue avelumab therapy. Hospitalize. Pulmonary and Infectious Disease consults. 1.0 to 2.0 mg/kg/day prednisone or equivalent Add prophylactic antibiotics for opportunistic infections Consider bronchoscopy, lung biopsy	Taper steroids over at least 1 month If not improving after 48 hours or worsening: Add additional immunosuppression (for example, infliximab, cyclophosphamide, IV	
Hepatic irAEs			
Grade of Liver Test Elevation	Initial Management	Follow-up Management	
Grade 1 Grade 1 AST or ALT > ULN to 3.0 × ULN and/or Total bilirubin > ULN to 1.5 × ULN	Continue avelumab therapy	Continue liver function monitoring If worsens: Treat as Grade 2 or 3 to 4.	
Grade 2 AST or ALT > 3.0 to ≤ 5 × ULN and/or total bilirubin > 1.5 to ≤ 3 × ULN			

Grade 3 to 4 AST or ALT > 5 × ULN and total bilirubin > 3 × ULN	Permanently discontinue avelumab therapy Increase frequency of monitoring to every 1 to 2 days 1.0 to 2.0 mg/kg/day prednisone or equivalent Add prophylactic antibiotics for opportunistic infections Consult gastroenterologist/hepatologist Consider obtaining MRI/CT scan of liver and liver biopsy if clinically warranted	Taper steroids over at least 1 month If does not improve in > 3 to 5 days, worsens or rebounds: Add mycophenolate mofetil 1 gram (g) twice daily If no response within an additional 3 to 5 days, consider other		

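### After a Grade 3 or higher liver-test event attributed to M6620, Sections 5.2.5.2 and 5.2.5.3.1 give incompatible instructions once the value is back to Grade 2, and 5.2.5.3.1 also contradicts itself on discontinuation

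*Combined protocol and SAP*

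**What the plan says.** Section 5.2.5.1 (Dose Interruptions) sends the reader elsewhere for restart: "Criteria required before treatment can resume are described in Dose Delays (Section 5.2.5.2". Section 5.2.5.3 does the same after a DLT.

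Section 5.2.5.2 (Dose Delays) has two relevant rules. For non-hematologic toxicity in general, item d lets a new cycle begin at baseline or "Grade ≤ 1 severity (or, at the investigator discretion, Grade ≤ 2 if not considered a safety risk for the patient". A separate sentence covers liver tests: "Withhold scheduled dose for liver function test related AEs (including asymptomatic) Grade" 3 or higher, and the hold lasts "until return to baseline or Grade" 1 or lower. That sentence carries no Grade 2 option. The section also says that both study drugs should be delayed together where applicable, so it is not confined to avelumab.

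Section 5.2.5.3.1, on M6620, gives several instructions:

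- After Grade 3 or higher M6620 toxicity, "treatment will be interrupted and may be resumed when all toxicities have returned to Grade 2 or lower, at the discretion of the Investigator". The only exclusions are fatigue, nausea, vomiting and diarrhea that supportive care controls.
- Items b and c of its first list discontinue M6620 for Grade 3 and Grade 4 non-hematologic toxicity respectively.
- Later text reduces M6620 by one dose level for Grade 3 non-hematologic toxicity, and lets it resume two levels lower once a Grade 4 non-hematologic toxicity is back to Grade 2 or lower.

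The note at the end of the general text in 5.2.5.3 lets the general rules give way to 5.2.5.3.2.1 and 5.2.5.3.2.2, both of which concern avelumab. It does not mention 5.2.5.3.1.

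**The concern.** The recovery level for restarting a drug is a patient-safety rule, and here its answer depends on the page consulted. A physician who treats 5.2.5.2 as the restart rule keeps the patient on hold at Grade 2. One who treats the M6620 section as the specific rule may restart. One who stops at items b and c discontinues M6620.

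There is also a consequence for the analysis. Safety and tolerability form the first primary objective (Section 2.1.1). While M6620 is weekly, each further week on hold costs one scheduled dose, and 5.2.5.1 does not replace doses omitted for toxicity within a cycle. M6620 exposure, and possibly discontinuation, would then partly reflect which instruction was followed.

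**Working it through.** No arithmetic applies, because the plan states no figure on this point. The check follows one patient through each instruction: a Grade 3 or higher liver-test event attributed to M6620, at successive stages of recovery.

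| Current liver-test grade | 5.2.5.2, liver-test sentence | 5.2.5.3.1, resume paragraph | 5.2.5.3.1, items b and c |
|---|---|---|---|
| Still 3 or higher, baseline lower | Hold | Hold | Discontinue |
| 2, baseline 1 or lower | **Hold** | **May restart, investigator's discretion** | **Discontinue** |
| 2, baseline already 2 | May restart | May restart, investigator's discretion | Discontinue |
| 1 or lower | May restart | May restart, investigator's discretion | Discontinue |

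The restart rules disagree only in the second row. The last column disagrees with the resume paragraph in every row, and with the later dose-level reductions in the same section, which presuppose that M6620 continues.

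**Size of the window, as illustration.** The hepatic part of Table 3 prints the Grade 2 range as "AST or ALT > 3.0 to ≤ 5 × ULN and/or total bilirubin > 1.5 to ≤ 3 × ULN". Table 3 manages immune-related events of avelumab, whereas Section 5.2.5 grades toxicity by CTCAE v5.0, whose cut-offs the documents do not print. The range shows what is at issue; the conflict itself rests on the grades in the text.

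**Who can be in the second row.** Inclusion criterion 12 allows bilirubin up to 1.5 × ULN, and AST/ALT up to 2.5 × ULN, or 5 × ULN with liver metastases. On the Table 3 cut-offs:

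- Without liver metastases, 2.5 is below 3, so baseline AST/ALT is Grade 1 or lower and the row applies.
- With liver metastases, baseline AST/ALT may already lie between 3 and 5 × ULN. Return to baseline then satisfies 5.2.5.2 at Grade 2, and the two restart rules agree.
- For bilirubin, the eligibility limit equals the top of Grade 1, so the row applies to everyone.

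**Does timing separate the rules?** Items a to d of 5.2.5.2 concern the start of a new cycle. The liver-test sentence concerns any scheduled dose, and M6620 is given on Days 1, 8, 15 and 22, so the conflict arises within a cycle too.

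**Other non-hematologic toxicity.** Item d allows Grade 2 at the investigator's discretion if it is not a safety risk. Section 5.2.5.3.1 allows Grade 2 at discretion without naming that condition. The difference in restart level is small.

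**The case against.** The strongest reply is that the rules can both be followed. Section 5.2.5.3.1 is permissive and describes its guidelines as a minimum, so a site that waits for baseline or Grade 1 breaches neither restart rule. Sections 5.2.5.1 and 5.2.5.3 point to 5.2.5.2, and the precedence note can be read as leaving 5.2.5.2 in force for M6620 because it does not exempt 5.2.5.3.1. This has weight: it would be too strong to say that the protocol gives no indication of which section governs. But the indication is indirect. Section 5.2.5.3.1 does not require waiting, has no liver exception and does not refer back to the liver-test sentence. A site that restarts at Grade 2 complies with 5.2.5.3.1 and departs from 5.2.5.2.

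A second reply is that item b means the example patient never restarts, so the restart level is moot. That holds only if items b and c prevail over the resume paragraph and the dose-level reductions, and the section does not say so. It allows exceptions to the first list by agreement between the PI and the IND Office, while the resume paragraph leaves restart to the investigator. The reply exposes a further contradiction and does not remove the first.

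Three wider readings are tempting and are not supported:

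- That the sections differ materially on restart for all non-hematologic toxicity. Item d's Grade 2 discretion nearly closes that gap.
- That the blood-count rules conflict. Section 5.2.5.2 uses numeric limits for a new cycle and 5.2.5.3.1 uses grades. Without printed CTCAE hematologic cut-offs, a conflict cannot be shown.
- That the difference decides the length of every hold and leads to a firm 28-day stop. It concerns the liver-test window above, and 5.2.5.2 allows case-by-case continuation after longer delays.

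**Conclusion.** The point holds, narrowly. For an M6620-related Grade 3 or higher liver-test event in a patient whose baseline was Grade 1 or lower, recovery to Grade 2 meets three incompatible instructions: stay on hold (5.2.5.2), restart at discretion (5.2.5.3.1), or discontinue (5.2.5.3.1, items b and c). The clash between discontinuing and resuming inside 5.2.5.3.1 is broader, since it covers Grade 3 and 4 non-hematologic toxicity generally.

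The instruction followed affects whether a hold continues, and may affect whether it reaches the 4-week limit in 5.2.5.2. The number of patients affected, and any effect on dose intensity or discontinuation rates, cannot be derived from the documents. The conclusion assumes that the liver-test sentence covers M6620, which its unrestricted wording and the instruction on delaying both drugs support. No view is taken on which rule is clinically right.

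**What to change.** The passages must be reconciled in two places:

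1. Reconcile the liver-test sentence of 5.2.5.2 with the resume paragraph of 5.2.5.3.1.
2. Within 5.2.5.3.1, reconcile items b and c with the later text on resumption and dose-level reduction. Aligning the restart level alone would leave this contradiction in place.

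The result should be one M6620 rule after Grade 3 or higher liver-test and other non-hematologic toxicity, cited from both sections, with the precedence note extended to say how 5.2.5.3.1 ranks against 5.2.5.2. The choice of rule belongs to the sponsor's clinical team. The cost is protocol amendment wording; sample size and analysis methods are unchanged.

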## 5.2.5.3.2 Adverse Drug Reactions Requiring Avelumab Treatment Discontinuation or Modifications

Treatment with avelumab should be permanently discontinued, if any of the following ADRs occurs:

Any Grade 4 ADRs:

• Permanently discontinue avelumab except for laboratory values out of normal range that do not have any clinical correlate.

Any Grade 3 ADRs:

- Withhold avelumab except for laboratory values out of normal range that do not have any clinical correlate;
- Permanently discontinue avelumab if toxicity does not resolve to Grade ≤ 1 or Baseline within 12 weeks of last administration or if the same Grade 3 toxicity recurs (consider consult with the Medical Monitor before permanently discontinuing the treatment).

If dosing is delayed more than 4 weeks, treatment may be resumed after consultation with the study Medical Monitor. Any delay in dosing in excess of 12 weeks is not permitted. Infusion-related reactions and irAEs should be handled according to guidelines as outlined in table below.

#### 5.2.5.3.2.1 Management of Infusion-Related Reactions

To mitigate infusion-related reactions associated with avelumab, participants have to be premedicated with an antihistamine and with paracetamol (acetaminophen) prior to the first 4 infusions of avelumab. Premedication should be administered for subsequent avelumab doses based upon clinical judgment and the presence/severity of prior infusion reactions.

Management of symptoms should follow the guidelines shown in Table 2.

Table 2: Treatment Modification for Symptoms of Infusion-related Reactions Associated with Avelumab.

NCI-CTCAE Grade Treatment Modification for Avelumab			
	Treatment Modification for Aveidinab		
Grade 1 – mild  • Mild transient reaction; infusion interruption not indicated.	Decrease the avelumab infusion rate by 50% and monitor closely for any worsening.		
Grade 2 – moderate  • Therapy or infusion interruption indicated but responds promptly to symptomatic treatment (for example, antihistamines, NSAIDs, narcotics, IV fluids); prophylactic medications indicated for ≤ 24 hours.	
 
Temporarily discontinue avelumab infusion.
 
Resume infusion at 50% of previous rate once infusion-related reaction has resolved or decreased to at least Grade 1 in severity, and monitor closely for any worsening.
 
		
Grade 3 or Grade 4 – severe or life-threatening  • Grade 3: Prolonged (for example, not rapidly responsive to symptomatic medication and/or brief interruption of infusion); recurrence of symptoms following initial improvement; hospitalization indicated for clinical sequelae.  • Grade 4: Life-threatening consequences; urgent intervention indicated.	
 
Stop the avelumab infusion immediately and disconnect infusion tubing from the participant.
 
Participants have to be withdrawn immediately from avelumab treatment and must not receive any further avelumab treatment.
 
		

IV=intravenous, NCI-CTCAE=National Cancer Institute-Common Terminology Criteria for Adverse Event, NSAIDs=nonsteroidal anti-inflammatory drugs.

#### 5.2.5.3.2.2 Immune-Related Adverse Events

Since inhibition of PD-L1 stimulates the immune system, irAEs may occur. Treatment of irAEs is mainly dependent upon severity (NCI-CTCAE v5 grade):

- Grade 1 to 2: treat symptomatically or with moderate dose steroids, more frequent monitoring
- Grade 1 to 2 (persistent): manage similar to high grade AE (Grade 3 to 4)
- Grade 3 to 4: treat with high dose corticosteroids

Treatment of irAEs should follow guidelines as shown in Table 3.

Table 3: Management of Immune-Related Adverse Events

Gastrointestinal irAEs						
Severity of Diarrhea/Colitis	Severity of Diarrhea/Colitis Initial Management Follow-up Management					
Grade 1 Diarrhea: < 4 stools/day over Baseline Colitis: asymptomatic	Continue avelumab therapy Symptomatic treatment (e.g., loperamide)	Close monitoring for worsening symptoms Educate participant to report worsening immediately If worsens: Treat as Grade 2, 3 or 4.				
Grade 2 Diarrhea: 4 to 6 stools per day over Baseline; IV fluids indicated < 24 hours; not interfering with ADL Colitis: abdominal pain; blood in stool	Withhold avelumab therapy Symptomatic treatment	If improves to Grade ≤ 1: Resume avelumab therapy  If persists > 5 to 7 days or recurs:  Treat as Grade 3 or 4.				

incontinence; IV fluids ≥ 24 h; interfering with ADL	Grade 3. Permanently discontinue avelumab for Grade 4 or recurrent Grade 3.	at least 1 month; resume avelumab therapy following
Colitis (Grade 3): severe abdominal pain, medical intervention indicated, peritoneal signs Grade 4: life-threatening, perforation	1.0 to 2.0 mg/kg/day prednisone IV or equivalent Add prophylactic antibiotics for	•

## Dermatological irAEs

Grade of Rash	Initial Management	Follow-up Management	
Grade 1 to 2 Covering ≤ 30% body surface area	Continue avelumab therapy. Symptomatic therapy (for example, antihistamines, topical steroids)		
Grade 3 to 4 Grade 3: Covering > 30% body surface area; Grade 4: Life-threatening consequences	Permanently discontinue for	Taper steroids over at least	

Pulmonary irAEs			
Grade of Pneumonitis	Initial Management	Follow-up Management	
Grade 1 Radiographic changes only	Consider withholding avelumab therapy Monitor for symptoms every 2 to 3 days Consider Pulmonary and Infectious Disease consults	Treat as Grade 2 or Grade	
Grade 2 Mild to moderate new symptoms	Withhold avelumab therapy Pulmonary and Infectious Disease consults Monitor symptoms daily; consider hospitalization 1.0 to 2.0 mg/kg/day prednisone or equivalent Add prophylactic antibiotics for opportunistic infections Consider bronchoscopy, lung biopsy	over at least 1 month, and then resume avelumab therapy following steroids taper If not improving after 2	
Grade 3 to 4 Grade 3: Severe new symptoms; New/worsening hypoxia; Grade 4: Life-threatening	Permanently discontinue avelumab therapy. Hospitalize. Pulmonary and Infectious Disease consults. 1.0 to 2.0 mg/kg/day prednisone or equivalent Add prophylactic antibiotics for opportunistic infections Consider bronchoscopy, lung biopsy	Taper steroids over at least 1 month If not improving after 48 hours or worsening: Add additional immunosuppression (for example, infliximab, cyclophosphamide, IV	
Hepatic irAEs			
Grade of Liver Test Elevation	Initial Management	Follow-up Management	
Grade 1 Grade 1 AST or ALT > ULN to 3.0 × ULN and/or Total bilirubin > ULN to 1.5 × ULN	Continue avelumab therapy	Continue liver function monitoring If worsens: Treat as Grade 2 or 3 to 4.	
Grade 2 AST or ALT > 3.0 to ≤ 5 × ULN and/or total bilirubin > 1.5 to ≤ 3 × ULN			

Grade 3 to 4 AST or ALT > 5 × ULN and total bilirubin > 3 × ULN	Permanently discontinue avelumab therapy Increase frequency of monitoring to every 1 to 2 days 1.0 to 2.0 mg/kg/day prednisone or equivalent Add prophylactic antibiotics for opportunistic infections Consult gastroenterologist/hepatologist Consider obtaining MRI/CT scan of liver and liver biopsy if clinically warranted	Taper steroids over at least 1 month If does not improve in > 3 to 5 days, worsens or rebounds: Add mycophenolate mofetil 1 gram (g) twice daily If no response within an additional 3 to 5 days, consider other		
Renal irAEs  Grade of Creatinine Increase	nd Initial Management	Follow-up Management		
Grade 1 Creatinine increase 1.5	× sed Continue avelumab therapy	Continue renal function monitoring If worsens: Treat as Grade 2 to 3 or 4.		
Grade 2 to 3 Creatinine increased > 1.5 baseline and ≤ 6 x ULN	Withhold avelumab therapy Increase frequency of or monitoring to every 3 days and 1.0 to 2.0 mg/kg/day prednisone or equivalent. Add prophylactic antibiotics for opportunistic infections Consider renal biopsy	If returns to Grade ≤1: Taper steroids over at least 1 month, and resume avelumab therapy following steroids taper.		
Grade 4 Creatinine increased > 6 × UL	Permanently discontinue  N avelumab therapy Monitor creatinine daily 1.0 to 2.0 mg/kg/day prednisone or equivalent. Add prophylactic antibiotics for opportunistic infections Consider renal biopsy Nephrology consult			
Cardiac irAEs	Cardiac irAEs			
Myocarditis	Initial Management	Follow-up Management		

New onset of cardiac signs or symptoms and/or new laboratory cardiac biomarker elevations (e.g., troponin, CK-MB, BNP) or cardiac imaging abnormalities suggestive of myocarditis.		avelumab therapy.  If symptoms do not improve/worsen, viral myocarditis is excluded, and immune-mediated etiology is suspected or confirmed following cardiology consult, manage as immune-mediated
Immune-mediated myocarditis	Permanently discontinue avelumab. Guideline based supportive treatment as appropriate as per cardiology consult. a 1.0 to 2.0 mg/kg/day prednisone or equivalent Add prophylactic antibiotics for opportunistic infections.	steroids over at least 1 month.  If no improvement or worsening, consider additional

a Local guidelines, or e.g., ESC or AHA guidelines ESC guidelines website: https://www.escardio.org/Guidelines/Clinical-Practice-Guidelines AHA guidelines website:

https://professional.heart.org/professional/GuidelinesStatements/UCM 492626 Guidelines-Statements-Search-Page.jsp

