For subjects whose dose was withheld due to toxicity, subjects may resume immunotherapy study drug (avelumab) upon resolution of toxicity to Grade 0-1 or baseline.

Note: The general treatment recommendations outlined in Sections  $\underline{5.2.5.1}$ ,  $\underline{5.2.5.2}$ , and  $\underline{5.2.5.3}$  can be used **unless** more specific treatment guidelines are outlined in Sections  $\underline{5.2.5.3.2.1}$  and  $\underline{5.2.5.3.2.2}$  below.

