Other irAEs (not described al	threatening symptoms of hypophysitis and/or abnormal MRI. Consider hospitalization. Initiate corticosteroids (1 to 2 mg/kg/day prednisone or equivalent) followed by corticosteroids taper during at least 1 month.  • Add prophylactic antibiotics for opportunistic infections.	
Grade of other irAEs	Initial Management	Follow-up Management
Grade 2 or Grade 3 clinical signs or symptoms suggestive of a potential irAE	Withhold avelumab therapy pending clinical investigation	If irAE is ruled out, manage as appropriate according to the diagnosis and consider restarting avelumab therapy If irAE is confirmed, treat as Grade 2 or 3 irAE.
Grade 2 irAE or first occurrence of Grade 3 irAE	Withhold avelumab therapy 1.0 to 2.0 mg/kg/day prednisone or equivalent Add prophylactic antibiotics for opportunistic infections Specialty consult as appropriate	If improves to Grade ≤ 1:  Taper steroids over at least 1 month and resume avelumab therapy following steroids taper.
Recurrence of same Grade 3 irAEs	Permanently discontinue avelumab therapy 1.0 to 2.0 mg/kg/day prednisone or equivalent Add prophylactic antibiotics for opportunistic infections Specialty consult as appropriate	If improves to Grade ≤ 1: Taper steroids over at least 1 month.
Grade 4	Permanently discontinue avelumab therapy 1.0 to 2.0 mg/kg/day prednisone or equivalent and/or other immunosuppressant as needed Add prophylactic antibiotics for opportunistic infections Specialty consult.	If improves to Grade ≤ 1: Taper steroids over at least 1 month
Requirement for 10 mg per day or greater prednisone or equivalent for more than 12 weeks for reasons other than hormonal replacement for adrenal insufficiency	Permanently discontinue avelumab therapy Specialty consult	

Persistent Grade 2 or 3 irAl	
asting 12 weeks or longer	

ADL=activities of daily living, AHA=American Heart Association, ALT=alanine aminotransferase, AST=aspartate aminotransferase, BNP=B-type natriuretic peptide, CK-MB=creatine kinase MB, CT= computed tomography, ESC=European Society of Cardiology, FSH=follicle stimulating hormone, GH=growth hormone, IGF-1=insulin-like growth factor 1, irAE=immune-related adverse event, IV=intravenous, LH=luteinizing hormone, MRI=magnetic resonance imaging, NCI-CTCAE=National Cancer Institute-Common Terminology Criteria for Adverse Events, PRL=prolactin, T4=thyroxine, TSH=thyroid-stimulating hormone, ULN=upper limit of normal.

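### Table 3's Grade 3–4 hepatic row requires both AST/ALT and bilirubin to be high, unlike the rows below it, and the fallback rules for asymptomatic high-grade liver tests are not aligned

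*Combined protocol and SAP*

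**What the plan says.** Table 3 in section 5.2.5.3.2.2 has three hepatic rows:

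- Lowest row, for Grade 1 events: "AST or ALT > ULN to 3.0 × ULN and/or Total bilirubin > ULN to 1.5 × ULN". Avelumab is continued.
- Middle row, for Grade 2 events: "AST or ALT > 3.0 to ≤ 5 × ULN and/or total bilirubin > 1.5 to ≤ 3 × ULN". As in the row before it, one test alone is enough to qualify.
- Top row, covering Grades 3 and 4 together, where the wording changes: "AST or ALT > 5 × ULN and total bilirubin > 3 × ULN". Avelumab is permanently discontinued.

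Four other places bear on the same patient:

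- **Section 5.2.5.3, closing note.** The general recommendations of 5.2.5.1 to 5.2.5.3 are available except where, in the note's words, "more specific treatment guidelines are outlined in Sections". The two sections it then names are those on infusion reactions and on immune-related events; the latter contains Table 3.
- **Section 5.2.5.2.** The liver-test rule opens: "Withhold scheduled dose for liver function test related AEs (including asymptomatic". It applies from Grade 3 upwards, and the hold lasts until baseline or Grade 1 or lower.
- **Section 5.2.5.3.2.** The rule for Grade 3 reactions is: "Withhold avelumab except for laboratory values out of normal range that do not have any clinical correlate". The rule for Grade 4 carries the same exemption but a stronger action: "Permanently discontinue avelumab except for laboratory values out of normal range that do not have any clinical correlate". The section ends by sending immune-related events to the table.
- **Section 5.2.5.** Where there are several toxicities, the worst one determines the dose modification.

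Table 3 also closes with a block for immune-related events not covered earlier in the table. One of its rows is "Grade 2 irAE or first occurrence of Grade 3 irAE", for which avelumab is withheld.

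**The concern.** The connector changes at the row with the most serious consequence. Below it, either test alone can place a patient in a row. At Grade 3–4, one very abnormal test is not enough. Because the Grade 2 row stops at 5 × ULN for AST/ALT and 3 × ULN for bilirubin, a single test above its limit has no natural place in the table.

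The pattern is foreseeable. Inclusion criterion 12 admits patients with liver metastases at AST/ALT up to 5 × ULN and requires bilirubin no higher than 1.5 × ULN. Such a patient can start at the top of the Grade 2 transaminase range with normal bilirubin, and any further AST/ALT rise leaves that range. Elsewhere the protocol treats AST/ALT elevation alone as important: for patients with hepatic metastases, section 3.3 counts AST/ALT above 8 × ULN, or above 5 × ULN for at least 14 days, as dose-limiting, with no bilirubin condition.

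The first stake is patient safety, since two clinicians applying the text in good faith could handle the same result differently. The second is the data. Safety and tolerability are a primary objective, and uneven handling of hepatic events feeds into exposure and adverse-event summaries.

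**Working it through.** The plan gives no figure to reproduce. The check is whether the three rows cover every combination of the two tests.

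**Inputs.** Let A be AST or ALT, and B total bilirubin, each as a multiple of ULN. The printed rows become:

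- Grade 1: 1 < A ≤ 3 **or** 1 < B ≤ 1.5
- Grade 2: 3 < A ≤ 5 **or** 1.5 < B ≤ 3
- Grade 3–4: A > 5 **and** B > 3

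**Rows met, as printed**

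| | B ≤ 1 | 1 < B ≤ 1.5 | 1.5 < B ≤ 3 | B > 3 |
|---|---|---|---|---|
| A ≤ 1 | none | G1 | G2 | **none** |
| 1 < A ≤ 3 | G1 | G1 | G1 and G2 | **G1 only** |
| 3 < A ≤ 5 | G2 | G1 and G2 | G2 | **G2 only** |
| A > 5 | **none** | **G1 only** | **G2 only** | G3–4 |

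An illustrative case is A = 10, B = 1.2. Grade 3–4 fails because 1.2 is not above 3. Grade 2 fails on both limbs. Grade 1 is met because 1 < 1.2 ≤ 1.5. The only row met is the one that continues avelumab.

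**Count.** Four cells have A > 5 and four have B > 3. They share one cell, so 4 + 4 − 1 = 7 cells have at least one test above its top limit. One meets Grade 3–4, two meet no row, and four meet only a lower row (two Grade 1, two Grade 2): 1 + 2 + 4 = 7.

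**Is the connector the cause?** As a test only, not a recommendation, replace *and* with *or* in the Grade 3–4 condition. All seven cells then meet that row, and the only cell meeting none is A ≤ 1 with B ≤ 1, where nothing is abnormal. But the four cells that met only a lower row now meet two rows, and the two G1-and-G2 cells remain: 4 + 2 = 6 cells with double membership. The connector therefore explains the gap, but changing it alone would not give one row per combination, because the table does not say which value governs.

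**The fallback, side by side, for an asymptomatic Grade 3 or higher liver test**

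| Place | Scope | Effect |
|---|---|---|
| 5.2.5.2 | liver tests, scheduled dose | withhold, symptoms or not |
| 5.2.5.3.2, Grade 3 | any reaction, avelumab | exempt from withholding if no clinical correlate |
| 5.2.5.3.2, Grade 4 | any reaction, avelumab | exempt from permanent discontinuation if no clinical correlate |

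The note in 5.2.5.3 ranks the specific guidelines above the general ones. It does not rank 5.2.5.2 against 5.2.5.3.2.

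**The case against.** The strongest reply is that the protocol already leads a careful reader to an answer. If Table 3 has no matching row, the note in 5.2.5.3 opens the general rules. Section 5.2.5.2 then has a liver-specific instruction and asks that a hepatologist's advice be considered in potential liver injury. Section 5.2.5 says the worst toxicity decides, which counts against managing a patient with AST/ALT above 5 × ULN under the Grade 1 row. Section 5.2.5.3.2.2 says treatment of immune-related events depends mainly on CTCAE grade. The closing block of Table 3 might also catch whatever the hepatic rows miss.

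Much of this stands, and it rules out three stronger readings:

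- A reader might infer that every combination of AST/ALT above 5 × ULN with bilirubin up to 3 × ULN is unassigned. The grid shows otherwise: only bilirubin at or below ULN meets no row. The other two bands fall into a lower row, which is under-grading by the table's own cut-offs.
- A reader might infer that the general rules do not reach the case. They do, through the note in 5.2.5.3.
- A reader might infer that the protocol orders opposite actions. It does not. Section 5.2.5.3.2 exempts certain laboratory values from a mandatory step; it does not instruct that avelumab be continued.

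The reply still does not settle the case. No sentence says that the liver-specific 5.2.5.2 prevails over the avelumab-specific 5.2.5.3.2. The worst-toxicity rule sits outside the table and does not say how two liver tests within one row are to be combined. The closing block is headed as covering events not described above it, and hepatic events are described above it.

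There is also a caution about the text. Table 3 is damaged in the machine-read copy: the Grade 2 hepatic action cells are blank and the Grade 3–4 follow-up cell is cut short. The Grade 3–4 criterion reads as a complete phrase and the other two rows kept *and/or*, but a lost *or* cannot be excluded without the PDF.

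**Conclusion.** The concern holds as an internal inconsistency in two parts. First, as printed, the Grade 3–4 hepatic row captures one of the seven band combinations with a test above its top limit; four go to a lower row and two to none. Second, the rules that would apply as a fallback are not aligned for asymptomatic high-grade liver tests, and their order is not stated.

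The first part assumes that the printed *and* is what the source PDF says and that the rows are read literally. The second does not depend on that connector: sections 5.2.5.2 and 5.2.5.3.2 would still need aligning if an *or* was lost. The counts are of table cells, not patients; how often such results would occur cannot be derived from the documents. The documents do not reproduce the CTCAE liver cut-offs, so no use is made of them, and nothing rests on the blank Grade 2 action cells. No view is taken on which clinical rule is right.

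**What to change.** Check the Grade 3–4 hepatic criterion in the source PDF. Then reconcile that row with the Grade 1 and Grade 2 rows and with sections 5.2.5.2 and 5.2.5.3.2. Two statements are needed: which row applies when AST/ALT and bilirubin point to different ones, and which passage governs an asymptomatic high-grade liver test. The revised text can be tested against the 4 × 4 grid above: every abnormal cell should lead to one row and one instruction. The sponsor decides what those instructions are.

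The cost is limited rewording of the hepatic rows and a cross-reference between the sections. No change to the sample size, stopping boundaries or planned analyses follows from it.
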